5.8. Safety Analyses

Safety analyses will be conducted using the Safety Population.

5.8.1. Adverse Events

Safety and tolerability will be assessed in terms of AEs, SAEs, laboratory data and vital signs, which will be collected for all subjects. The AE term (Investigator term) will be assigned to the lowest level term (LLT), and a preferred term (PT) will be classified by a high level term (HLT), a high level group term (HLGT) and a system organ class (SOC) according to the Medical Dictionary for Regulatory Activities (MedDRA) thesaurus, Version 15.1 or higher depending on the latest version available during the study. The intensity of AEs will be graded according to the NCI-CTCAE (version 4.0).

An overview of the number of patients with AEs and the corresponding number of AEs will be presented through tables and listings:

- Total AE count
- Any AE
- Any treatment-related AE (Cytarabine and/or GRASPA®)
- Any AE of CTCAE grade ≥ 3
- Any AE of CTCAE grade = 4
- Any treatment-related (Cytarabine and/or GRASPA®) AE of CTCAE grade ≥ 3
- Any severe treatment-related (Cytarabine and/or GRASPA®) AE
- Any AE with outcome of death
- Any serious AE

- Any treatment-related (Cytarabine and/or GRASPA®) serious AE
- Any AE leading to permanent discontinuation
- Any treatment-related (Cytarabine and/or GRASPA®) AE leading to permanent discontinuation (Action taken=Withdrawn)
- Any AE leading to temporary discontinuation
- Any treatment-related (Cytarabine and/or GRASPA®) AE leading to temporary discontinuation (Action taken=Reduced)

An AE will be considered as “treatment-related” if the relationship to study treatment is ticked “possible,” “probable” or “certain/definite”.

For subject counts, subjects are included only once, even if they experienced multiple events in that category.

All the following summaries will be displayed by treatment groups on the safety population:

- All AE by System Organ Class (SOC) term, Preferred Term (PT)
- AE Experienced by $\geq 5\%$ of Subjects by SOC term and PT
- Treatment-related (Cytarabine and/or GRASPA®) AE by SOC term and PT
- AE of CTCAE grade ≥ 3 by SOC term and PT
- AE of CTCAE grade = 4 by SOC term and PT
- Treatment-related (Cytarabine and/or GRASPA®) AE of CTCAE grade ≥ 3 by SOC term and PT
- Severe treatment-related (Cytarabine and/or GRASPA®) AE by SOC term and PT
- AE with outcome of death
- Serious AE
- Treatment-related (Cytarabine and/or GRASPA®) serious AE
- AE leading to permanent discontinuation
- AE leading to temporary discontinuation

Serious AE, AE with outcome of death and AE leading to permanent or temporary discontinuation will also be described on an individual basis: treatment group, patient's code, sex and age, investigator's reported term, preferred term, date of onset, NCI-CTCAE Criteria Grading, intensity, outcome, seriousness, suspected relationship regarding Cytarabine and GRASPA®, action taken, corrective therapy.

A special focus will be put on diabetogenic and pancreatic adverse events based on the following table:

	GRASPA + LDAC n(%)	LDAC n(%)	Total n(%)
Number of patients with xxx adverse events	xx (x.x%)	xx (x.x%)	xx (x.x%)
PT1	x (x.x%)	x (x.x%)	x (x.x%)
PT2	x (x.x%)	x (x.x%)	x (x.x%)
Number of events	xx	xx	xx
Events characteristics, n			
Serious	x (x.x%)	x (x.x%)	x (x.x%)
Cytarabine-related	x (x.x%)	x (x.x%)	x (x.x%)
GRASPA®-related	x (x.x%)	x (x.x%)	x (x.x%)
Permanent discontinuation of Cytarabine	x (x.x%)	x (x.x%)	x (x.x%)
Permanent discontinuation of GRASPA	x (x.x%)	x (x.x%)	x (x.x%)
Fatal	x (x.x%)	x (x.x%)	x (x.x%)
Number of occurrences, n			
One	x (x.x%)	x (x.x%)	x (x.x%)
Two or more	x (x.x%)	x (x.x%)	x (x.x%)
Maximum toxicity grade, n			
Grade 1	x (x.x%)	x (x.x%)	x (x.x%)
Grade 2	x (x.x%)	x (x.x%)	x (x.x%)
Grade 3	x (x.x%)	x (x.x%)	x (x.x%)
Grade 4	x (x.x%)	x (x.x%)	x (x.x%)
Outcome, n			
Resolved	x (x.x%)	x (x.x%)	x (x.x%)
Not resolved	x (x.x%)	x (x.x%)	x (x.x%)
Fatal	x (x.x%)	x (x.x%)	x (x.x%)
Action taken with cytarabine, n			
Dose not changed	x (x.x%)	x (x.x%)	x (x.x%)
Temporarily interrupted	x (x.x%)	x (x.x%)	x (x.x%)
Permanently discontinued	x (x.x%)	x (x.x%)	x (x.x%)
Not applicable	x (x.x%)	x (x.x%)	x (x.x%)
Action taken with GRASPA®, n			
Dose not changed	x (x.x%)	x (x.x%)	x (x.x%)
Temporarily interrupted	x (x.x%)	x (x.x%)	x (x.x%)
Permanently discontinued	x (x.x%)	x (x.x%)	x (x.x%)
Not applicable	x (x.x%)	x (x.x%)	x (x.x%)

Diabetogenic effects will comprise diabetes mellitus, glucose and lipid increase. Pancreatic events will comprise clinical pancreatitis and asymptomatic (biochemical) pancreatitis.

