8.5.3 Dosage modifications for cytarabine

- Cytarabine dosage modifications should be applied according to the prescribing information and standard practice. At investigator judgment, if required by patient status, cytarabine dosage increase is acceptable.
- A standard recommendation, in case of toxicity attributed to cytarabine, is to reduce the dosage of cytarabine to 20 mg daily.
- In case of persistent or excessive toxicity attributed to cytarabine, cytarabine may be temporarily or permanently discontinued, as per investigator judgment. In such case, for patients in arm B, GRASPA should be continued as scheduled, every 14 days.

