11.1.2.2 Recording procedure

Any event meeting the definition of an AE / SAE must be collected and reported from subject signature of the informed consent and until 4 months after last GRASPA/ low-dose cytarabine administration (see Figure 4).

Any AE / SAE related to GRASPA according to investigator's opinion must be collected and reported throughout study duration.

Any SAE leading to death or life threatening must be collected and reported throughout study duration. **Figure 4: Safety reporting timeline guide**

All AE / SAE must be followed until resolution or the end of the protocol. The Investigator should ensure that adequate medical care is provided to the subject for any adverse event.

If there are several events and different symptoms combined to a main AE, then the only main AE (diagnostic preferable if available) should be recorded in the CRF. Where there is no link between different clinical symptoms occurring at the same time, each sign should be recorded as separate AE.

Occurrence and follow-up of AE should be assessed at each visit, and essential data listed hereafter should be recorded in the patient's CRF and patient's medical file as well:

- the severity or grade of the adverse event,
- the causality: determination of whether an adverse event is related to the investigational treatment or procedure, or other agents are suspected of causing the adverse event,
- the action(s) taken regarding investigational product (continued / interrupted / stopped)
- the corrective treatment if any
- the event outcome
- the seriousness of the event

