	Patient i	nitials : Last nam	· ne First name	Patient No	: - Site No Patient .	 No		
II. STUDY TR	REATMENT IN	NFORMATION	N					
14. Treatment :	$\Box GR$	PASPA®	🗌 NA					
15. Dose (per infusion)	16. Route	Number of infusions	18. 1 st infusion	date :	18. l a	ast infusion da	ate :	
UI/kg.			Day Month	 Year	 Day	Month Y	 Tear	
Action taken r	egarding study	treatment :	20. Did event abate after	stopping	Relationship to s	tudy treat	ment :	
None, Dose not	t changed (drug con	tinued)		NT / 11 11	No Reasonable Possi	bility :	_	
Drug withdraw	n (drug stopped)			Not applicable	Not applicable	Not relate	ed 🗌 Unlik	ely
Dose reduced (or drug transitory d	liscontinued)	21. Did event reappear a reintroduction :	ufter Not applicable	Reasonable Possibility : Possible Probable Certain / Definite			
14 Treatment	$\Box CV$	TARARINF			∐ Not assessable			
15. Dose (per	16 Route	Number of	18 1 st administration	on date :	18 last	administration	n date :	
administration)	10. Route	administration						
Action taken r		treatment ·	Day Month	Year stopping	Day Month Year			
None. Dose not	t changed (drug con	tinued)	treatment	stopping	No Reasonable Possibility :			
Drug withdraw	n (drug stopped)	,	Yes No Not applicable		Not applicable Not related Unlikely			
Dose reduced (or drug transitory discontinued)			21. Did event reappear	after	Reasonable Possibility :			
Not applicable			reintroduction : Possible Probable Certain / Definite Yes No Not applicable					
					Not assessable			
III. MEDICAI	L HISTORY A	ND ASSOCIA	FED MEDICATION					
23. Relevant me	edical history:						□ None	
22. Concomitan	its medication ((except those fo	or event treatment) :	Start Data	Ster Dete		□ None	- 41
(generic name)	(daily)	Route	Indication (e	dd/mm/yyyy)	(dd/mm/yyyy)	On going	event	t the
							Yes	🗌 No
							Yes	🗌 No
							Yes	🗌 No
							Yes	🗌 No
							Yes	🗌 No
							□Yes	🗌 No
							□Yes	🗌 No
							Yes	No
							Yes	No
Investigator co	ompleting the r	eport (Name an	id address) : Sig	gnature			1	

- CONFIDENTIAL -

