7. REFERENCES

8. CLINICAL STUDY REPORT APPENDICES

8.1. Statistical Tables, Figures, and Listings to be Generated

Table/Figure Number	Output Title	Analysis Set
	Patient Information	
14.1.1.1	Overall Patients Disposition	All Patients
14.1.1.2	Patients Disposition by Investigator Centre	All Patients
	Protocol Deviations	
14.1.2.1	Summary of Deviations Related to Inclusion/Exclusion Criteria	ITT
14.1.2.2	Summary of Major Protocol Deviations – Reasons for Exclusion From Per Protocol Population	ITT
14.1.2.3	Listing of Patients Randomized but not Treated	ITT
	Demographic Data and Baseline Characteristics	
14.1.3.1	Patient Demographics and Baseline Characteristics	ITT
14.1.3.2	Disease Characteristics and AML Cancer History	ITT
	Prior Related Therapies	
	Medical History Related to Other Diseases	

Table/Figure Number	Output Title	Analysis Set
14.1.4.1	Summary of Medical History – Previous Condition	ITT
14.1.4.2	Summary of Medical History – Ongoing Condition	ITT
	Prior and Concomitant Medications	
14.1.5.1	Summary of Prior Medications	ITT
14.1.5.2	Summary of Concomitant Medications	ITT
	Treatment Compliance and Exposure	
14.1.6.1	Summary of Study Duration	Safety
	Treatment Exposure	
14.1.6.2.1	Summary of Exposure to GRASPA and Low Dose Cytarabine and Dose Intensity	Safety
14.1.6.2.2	Compliance, Dose Reductions and Interruptions of GRASPA and Low Dose Cytarabine	Safety
14.1.6.2.3	Listing of Patients with at Least One Dose Reduction or Interruption of GRASPA and Low Dose Cytarabine	Safety
	Efficacy Data	
14.2.1.1.1.1	Summary of Overall Survival by Treatment Group	ITT

Table/Figure Number	Output Title	Analysis Set
14.2.1.1.1.2	Summary of Overall Survival by Treatment Group	PP
14.2.1.1.2.1	Overall Survival by Treatment Group – Kaplan Meier Curves	ITT
14.2.1.1.2.2	Overall Survival by Treatment Group – Kaplan Meier Curves	PP
14.2.1.1.3.1	Summary of Overall Survival by Treatment Group – Cox PH Model with Prognostic Factors	ITT
14.2.1.1.3.2	Summary of Overall Survival by Treatment Group – Cox PH Model with Prognostic Factors	PP
14.2.1.1.4.1	Forest Plot of OS Hazard Ratios – Subgroup Analyses	ITT
14.2.1.1.4.2	Forest Plot of OS Hazard Ratios – Subgroup Analyses	PP
14.2.1.2.1.1	Summary of Disease Response and Duration of Response by Treatment Group	ITT
14.2.1.2.1.2	Summary of Disease Response and Duration of Response by Treatment Group – Subgroup Analyses	ITT
14.2.1.3.1.1	Summary of Progression Free Survival by Treatment Group	ITT

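### SAP 5.8.1 reports cytarabine dose reductions as temporary discontinuations, and its discontinuation rows do not say which drug was changed

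*SAP*

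**What the plan says.** The overview list in SAP 5.8.1 has four rows on discontinuation, two permanent and two temporary, each in an all-event and a treatment-related form.

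- The treatment-related temporary row is "AE leading to temporary discontinuation (Action taken=Reduced").
- The matching all-event row is "Any AE leading to temporary discontinuation" and carries no code.
- The treatment-related permanent row is "AE leading to permanent discontinuation (Action taken=Withdrawn"). Its all-event counterpart again has no code.

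None of the four names the drug that was stopped or changed. The bracket naming cytarabine and/or GRASPA in the treatment-related rows belongs to the causality judgement.

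Protocol 8.5.3 says that a standard recommendation, "in case of toxicity attributed to cytarabine, is to reduce the dosage of cytarabine to 20 mg daily". Temporary or permanent discontinuation is a separate step, for toxicity that persists or is excessive.

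The SAE form (Protocol Appendix 7) offers, once for each drug, the box "Dose reduced (or drug transitory discontinued"). Protocol 11.1.2.2 asks for "the action(s) taken regarding investigational product (continued / interrupted / stopped"). The table in SAP 5.8.1 for diabetogenic and pancreatic events has an action block per drug, with "Temporarily interrupted" but no row for a reduced dose.

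**The concern.** The protocol expects cytarabine reductions; the 20 mg adjustment also appears in the synopsis, in Protocol 10.1 and in SAP 3.1. Under the SAP's code, each adverse event handled by such a reduction alone, if judged treatment-related, goes into a row that a reader of the study report will take to mean that treatment was interrupted. The row then overstates interruption by an unknown amount.

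The second issue is the comparison between arms. Because no drug is named, a patient in the GRASPA arm can enter a discontinuation row through GRASPA or through cytarabine, and a control patient through cytarabine only. A reader who takes a higher figure in the GRASPA arm as poorer tolerance of cytarabine could be wrong, since the extra drug alone can produce it. Safety of the combination is a secondary objective, so these rows will be read.

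**Working it through.** The plan states no figure on this point, so there is none to reproduce. The check sets the sources side by side.

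| Source | How a dose change is classified |
|---|---|
| Protocol 8.5.3 (cytarabine) | Reduction and temporary stop are distinct |
| Protocol 8.5.4 (GRASPA) | Postponement, stopping an infusion, discontinuation; no reduced dose level |
| Protocol 11.1.2.2 | Continued, interrupted or stopped; no reduced category |
| SAE form | Withdrawn; reduced and transitory stop merged; one set of boxes per drug |
| SAP 5.8.1 overview, treatment-related rows | Withdrawn = permanent; Reduced = temporary discontinuation |
| SAP 5.8.1 overview, all-event rows | No code |
| SAP 5.8.1 diabetogenic and pancreatic table | Unchanged, interrupted, discontinued or not applicable; no reduced row |

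**Step 1, the label.** Take a patient with a cytarabine-related event who receives all ten injections of the next course at 20 mg. Under Protocol 8.5.3 this is a reduction. Under the SAP's treatment-related row the action is Reduced, so the patient is counted as temporarily discontinued. If the event is pancreatic, the special table has no row that fits.

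**Step 2, what the code contains.** The SAP code looks like a short form of the merged SAE-form box. If the AE page of the eCRF is built the same way, the row mixes reductions and interruptions. If that page has its own code for interruption, the row holds reductions only and misses the true interruptions. The AE page is not in the documents, so it is not known which applies. The label is wrong in either case.

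If the code is merged, the share of the row that is reduction equals r / (r + i), where r and i are the proportions of patients with a reduction only and with an interruption. Both are assumed here:

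- r = 5%, i = 5%: row 10%, of which 50% is reduction.
- r = 10%, i = 5%: row 15%, of which 67%.
- r = 20%, i = 5%: row 25%, of which 80%.

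**Step 3, the extra route.** Let each drug be stopped for an adverse event with probability p, the same for both drugs. An any-drug row then has probability p in the control arm and, under independence, 1 − (1 − p)² in the GRASPA arm. Planned arm sizes are 41 and 82 (SAP 5.1). The values of p are assumptions.

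| p | Control arm | GRASPA arm, independent | Ratio |
|---|---|---|---|
| 5% | 5% (about 2 of 41) | 1 − 0.95² = 9.75% (about 8 of 82) | 1.95 |
| 10% | 10% (about 4 of 41) | 1 − 0.90² = 19% (about 16 of 82) | 1.9 |
| 20% | 20% (about 8 of 41) | 1 − 0.80² = 36% (about 30 of 82) | 1.8 |

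Without independence, the GRASPA-arm figure lies between p (the same patients stop both drugs) and 2p (no overlap). At p = 10% that is 10% to 20%. The excess can therefore be anything from none to a doubling, with cytarabine tolerated equally in both arms.

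**The case against.** Much can be said for the plan.

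- **The cytarabine backbone is covered elsewhere.** A reader might infer that the tables cannot show whether adding GRASPA costs patients their cytarabine. The documents do not support that. SAP 8.1 plans an exposure and dose intensity table (14.1.6.2.1), a table titled "Compliance, Dose Reductions and Interruptions of GRASPA and Low Dose Cytarabine" (14.1.6.2.2) and a listing of patients with a reduction or interruption (14.1.6.2.3). Listing 16.2.5.1.2 gives cytarabine administration. This stands.
- **The SAP does not expressly pool the drugs.** That the action is pooled is an inference from rows that name no drug. It has some support from listing 14.3.1.3, which covers withdrawal of either GRASPA or chemotherapy. Against it, the diabetogenic and pancreatic table splits action by drug, the individual listings give relationship to each drug and action taken, and the output shells are in a separate document (SAP 1). The pooling is therefore likely but not certain.
- **An any-drug row is legitimate.** Having a second drug that may have to be stopped is part of the regimen's burden. To call the arms not comparable would go too far; the row is only not like for like for cytarabine.
- **The sources conflict less than they seem to.** The SAE form and the SAP code are compatible if Reduced abbreviates the merged box. Protocol 11.1.2.2 speaks of the investigational product, which can be read as GRASPA alone, a product with no reduced level. The special table covers two event groups only. This stands, but it leaves the overview label wrong for cytarabine.
- **Cytarabine dose increases**, which Protocol 8.5.3 permits, appear in no output title. That is a separate and optional matter.

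**Conclusion.** The concern holds in a limited form. On the treatment-related row, SAP 5.8.1 labels as temporary discontinuation a category that includes, and may consist only of, dose reductions. The all-event row has no definition. No overall summary of adverse events leading to a change of treatment is specified by drug, so a difference between arms in these rows cannot be attributed to cytarabine.

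The size cannot be given from the documents, which state no reduction, interruption or withdrawal rates. The percentages in the working show only how the arithmetic behaves under assumed rates; they do not predict this trial's results. The conclusion on the label needs no rates. The conclusion on the drugs assumes that the rows are filled by any study drug, as their wording suggests.

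A reader might go on to infer that the OS result is compromised. It is not: these are safety-table definitions and do not enter the OS analysis. The point merits correction before the SAP is signed, because it changes what the safety tables report.

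**What to change.** In SAP 5.8.1:

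1. State one action-taken definition, with its source field, and apply it to both the all-event and the treatment-related rows.
2. Check the AE page of the eCRF. If it separates reduction from interruption, show them as separate rows. If it merges them, label the row as dose reduced or temporarily interrupted, and take the split from table 14.1.6.2.2, built from the dosing records behind listings 16.2.5.1.1 and 16.2.5.1.2. Dosing records show what was given but not which event caused the change, so they should not be used to reassign individual adverse events.
3. Show the permanent-discontinuation and reduced or interrupted rows by drug, with cytarabine in both arms and GRASPA in the GRASPA arm only. Keep the any-drug rows beside them as the regimen-level summary.
4. Add the matching category to the diabetogenic and pancreatic table.

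The cost is some SAP and shell wording, a few more table rows and a little programming. No new data are needed.

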11.1.2.4 Causality assessment

Causality is the determination of whether an adverse event is related to a medical treatment or procedure. Causality categories are:

- **Reasonable possibility:** where the AE is clearly (certainly), likely to be (probably) or could be (possibly) related to the treatment or procedure.
- No reasonable possibility: where the AE is clearly NOT (not related) or doubtfully (unlikely) related to the treatment or procedure.
- In the case it is impossible to judge the AE causality, due to lack of information, or inconsistent information which cannot be investigated further, the AE/SAE will be reported as **possibly related**.

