5.2.8. Missing, Unused, and Spurious Data

In general, there will be no substitutions made to accommodate missing data points. All data recorded on the CRF will be included in data listings that will accompany the clinical study report.

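### SAP 5.8.1 has no place for events ticked 'Not assessable', so they fall out of the treatment-related counts although protocol 11.1.2.4 treats them as possibly related

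*SAP*

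**What the plan says.** Three texts bear on this.

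- **Protocol 11.1.2.4 (Causality assessment)** has two categories, reasonable possibility and no reasonable possibility, and a default. The default's condition is: "In the case it is impossible to judge the AE causality, due to lack of information, or inconsistent information which cannot be investigated further". Its consequence is: "the AE/SAE will be reported as possibly related". It covers serious and non-serious events.
- **Protocol Appendix 7 (SAE report form)** asks for the relationship to GRASPA and to cytarabine separately. For each drug the related group reads "Reasonable Possibility : Possible Probable Certain / Definite". The other group offers not applicable, not related and unlikely. Outside both groups stands a further box: "Not assessable".
- **SAP 5.8.1 (Adverse Events)** gives the counting rule: "An AE will be considered as “treatment-related” if the relationship to study treatment is ticked “possible,” “probable” or “certain/definite". This feeds outputs such as "Any treatment-related AE (Cytarabine and/or GRASPA").

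The SAP has no rule that recodes causality. Its general statement on gaps, in 5.2.8, is: "In general, there will be no substitutions made to accommodate missing data points".

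**The concern.** The SAP's rule names exactly the three boxes in the form's related group and omits the fourth box, which describes the situation that protocol 11.1.2.4 resolves conservatively. A programmer who follows 5.8.1 literally will leave such an event out of the related counts, where the protocol wants it in.

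Tolerability is in the study title and the safety of GRASPA in combination is a secondary objective, so related-event and related-SAE counts are outputs that readers will use. Events of unclear cause are foreseeable: protocol 11.2.1 itself provides for sudden death without a stated cause.

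**Working it through.** The plan attaches no figure to this rule, so there is none to reproduce. The check sets the texts side by side and then follows an event into the outputs.

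**Step 1. Each box under each rule, for one drug**

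| Box on the SAE form | Protocol 11.1.2.4 | SAP 5.8.1 as written |
|---|---|---|
| Possible, probable, certain/definite | related | related |
| Unlikely, not related | not related | not counted as related |
| Not applicable | not addressed | not counted as related |
| Not assessable | possibly related | not counted as related, by omission |

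Only in the last row does the SAP give a result contrary to the protocol.

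**Step 2. From drug-level ticks to outputs.** Most outputs in 5.8.1 combine the drugs (cytarabine and/or GRASPA). Drug-specific rows appear in the special-focus table for diabetogenic and pancreatic events; I assume that they apply the same three-box rule to the drug named.

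| Ticks for one SAE | Combined outputs | Drug-specific rows |
|---|---|---|
| GRASPA not assessable, cytarabine possible | counted | lost from the GRASPA row only |
| Cytarabine not assessable, GRASPA possible | counted | lost from the cytarabine row only |
| Both not assessable | lost | lost from both rows |
| One not assessable, the other unlikely or not related | lost | lost from the row of the drug not assessable |
| Control arm: cytarabine not assessable, GRASPA not applicable | lost | lost from the cytarabine row |

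The last column matters only for diabetogenic or pancreatic events. In the control arm a single tick removes the event from the combined outputs. In the GRASPA arm it is removed only if the other drug is not ticked related either.

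**Step 3. Outputs exposed.** These are the six treatment-related lines of the 5.8.1 overview, four treatment-related summaries in the list that follows it, the cytarabine-related and GRASPA-related rows of the special-focus table, and planned tables 14.3.1.1.2, 14.3.1.2.2, 14.3.1.2.4 and 14.3.1.2.6.

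**Step 4. Size.** The documents give no frequency for the box. With planned arm sizes as denominators, one patient lost from a related count moves the arm's percentage by:

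- GRASPA arm: 1/82 = 1.2 percentage points
- Control arm: 1/41 = 2.4 percentage points

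Purely as an illustration, assume that 20% of the GRASPA arm has a related SAE under the protocol rule: 0.20 × 82 = 16.4 patients. Let q be the share of these patients whose only qualifying events are ticked not assessable, with neither drug ticked related.

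| q (assumed) | Patients lost (16.4 × q) | Reported rate (20% × (1 − q)) |
|---|---|---|
| 5% | 0.8 | 19% |
| 10% | 1.6 | 18% |
| 20% | 3.3 | 16% |

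Neither the 20% nor q comes from the documents. Within each arm the direction is fixed: omission can only lower the count.

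**The case against.** The best reply is that protocol 11.1.2.4 acts when the event is reported. A site that follows it ticks possible, the SAP counts the event, and the box stays empty. On that reading the protocol text and the SAP agree, and the inconsistency lies inside the protocol, between 11.1.2.4 and its own form. The origin is rightly placed, but this does not remove the gap: the form offers the other answer, and the SAP has no rule for it if it is used.

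Three further points stand and limit the finding.

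- The box is documented only on the SAE form. Protocol 11.2.2 makes that form an addition to the CRF, and the SAP introduction lists the eCRF among its source documents. The eCRF page is not available. The SAP's term certain/definite matches the form rather than the wording of 11.1.2.4, which suggests a shared list but does not prove it.
- SAP 5.8.1 also tabulates events regardless of cause. It describes serious, fatal and discontinuation events individually, with the suspected relationship to each drug. Affected SAEs therefore stay visible.
- The illustrative patient numbers show scale and are not evidence.

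A reader might infer that the SAP reverses the protocol's rule and should have declared this in its section 6. The documents do not support that. The SAP never mentions the box, the exclusion follows from silence, and protocol 15.3.3 defines no related category from which the SAP could depart. A reader might also infer that such events vanish from every related output. Step 2 shows otherwise: one tick of possible for the other drug keeps the event in all combined outputs.

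**Conclusion.** The point holds as an unhandled category. Applied literally, SAP 5.8.1 leaves out of the related counts an SAE that protocol 11.1.2.4 would count. The loss affects the drug-specific rows whenever that drug is ticked not assessable, and the combined outputs when neither drug is ticked related. For non-serious events it is conditional on the eCRF having the same option.

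The number of events cannot be derived and could be zero. The conclusion rests on two assumptions: that the box, or its equivalent, reaches the analysis data, and that 5.8.1 is programmed as written.

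One might infer that the gap favours GRASPA. The documents do not show this. Related counts can only fall in each arm, but the comparison between arms can move either way, and the control arm needs only one tick for an event to be lost from the combined outputs. The primary endpoint is untouched. It is a modest correction, worth making before database lock.

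**What to change.** 1. In SAP 5.8.1, add that a relationship ticked not assessable counts as possibly related, in line with protocol 11.1.2.4. Apply this per drug, and only to drugs the patient actually received.
2. State that not applicable stays unrelated, for example GRASPA in arm A. Without this limit, control-arm events could be classed as GRASPA-related. A blank field is a different case, which 11.1.2.4 does not name, and should not be swept into the same rule.
3. Footnote the number of such events by arm under the related-event tables.
4. Align the Appendix 7 form with 11.1.2.4, and check whether the eCRF carries the same option.

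For the SAP the cost is a sentence, one programming condition and a footnote; the form needs a small revision. The downside is that related-event counts become slightly less favourable if the box was used. If it was never used, no count changes.
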